8.2.3 Suspected unexpected serious adverse reactions (SUSARs)

These will be dealt with as any serious adverse reaction as described as above.

8.3 Annual safety report

N.A.

8.4 Follow-up of adverse events

All AEs will be followed until they have abated, or until a stable situation has been reached. Depending on the event, follow up may require additional tests or medical procedures as indicated, and/or referral to the general physician or a medical specialist.

SAEs need to be reported till end of study within the Netherlands, as defined in the protocol.

8.5 Data and Safety monitoring board

Given the nature of this study a Data and Safety Monitoring Board (DSMB) is not required based on the FDA guidance document, "Establishment and Operation of Clinical Trial Data Monitoring Committees" and EMA guideline "Guideline on data monitoring committees". Monitoring of the data is requested and would be performed by a clinical research monitor (CTCM).

Cocogen Trial

9. STATISTICAL ANALYSIS

Patient baseline characteristics will be described for both knee pain groups separately, and stratified by treatment allocation using mean and standard deviation or median and interquartile range for continuous variables, and count and percentage for categorical variables. Incomplete patients records will be imputed using multiple imputation to allow analysis on all randomised subjects.

All outcome measures will be computed on the intention to treat sample.

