The transducer is placed in a coronal orientation on the lateral side of the proximal knee. After identifying the femoral lateral epicondyle, the transducer is displaced proximally to image the junction between the epiphysis and diaphysis of the femur and the vastus lateralis superficial to it. The superolateral genicular artery may or may not be seen between the deep fascia of the muscle and the femur at this level. If the superolateral genicular artery is visualised just above the bony cortex, the target point is next to this artery. If the artery is not visualised, the junction between the epiphysis and diaphysis is the target point. The probe-to-target point distance is assessed with ultrasound. An out-of-plane entry point is marked perpendicular to the center of the probe at the assessed probe-to-target point distance. Consecutively, the transducer was turned 90° into the transverse plane at this point. The skin and soft tissue are anesthetized with 1 ml lidocaine 2% at the estimated entry point. The

Cocogen Trial

cannula is advanced using an anterior to posterior 'in plane' approach in the transverse plane until contact is made with the bony cortex at the center of the femur. A RF electrode is introduced in the cannula. Sensory stimulation (50 Hz) is applied and produced paresthesia at a threshold of less than 0,5 V. The absence of fasciculations below 1 V is observed after motor stimulation at 2 Hz, confirming sufficient distance to relevant motor branches. If no sensory stimulation threshold is obtained at this position, If no sensory stimulation threshold is obtained at this position, the transducer is repositioned until sensory threshold is reached.

[figure not shown]

Fig. Ultrasound probe position and corresponding images for genicular radiofrequency treatment. Color Doppler shows the corresponding genicular arteries. Treatment sites are marked with yellow asterisks.

If all three target nerves were identified, a control fluoroscopy image is made to confirm the needle tip position. First, an AP view is made and the needle tip should be at the junction between the diaphysis and the epiphysis touching the bony cortex. Second, a lateral view is made where the needle tip should be within the 2 middle quarters of the femur width.

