- The change in health-related quality of life, measured by the change in EQ-5D-5L, between baseline and 6 and 12 months post intervention. (41) The EQ-5D-5L is a patient-reported generic measure of HRQoL comprising five dimensions: mobility, self-care, usual activities, pain/discomfort and anxiety/depression. Responses to the 5 items (one for each dimension) result in a patient's health state that can be transformed into a utility score ranging between 0 (death) and 1 (full health), representing the quality of life of the health state. (41). The EQ-5D-5L is assessed at baseline and at 1, 3, 6 and 12 months post intervention.
- Change in characteristic attitudes and symptoms of depression from baseline to 3, 6 and 12 months post intervention. This will be measured by the change in Hospital Anxiety and Depression Scale (HADS) and in Pain Catastrophizing Scale (PCS) from baseline to 6 and 12 months. (42, 43) HADS is developed to detect anxiety and depression in patients with physical health problems. The questionnaire consists of 14 items: 7 items to measure anxiety and 7 items to measure depression. The PCS is often used in clinical settings to measure catastrophic thinking related to pain. The 13 item questionnaire consists of 3 subscales (magnification, rumination and helplessness) and asks patients to

Cocogen Trial

reflect on past painful experiences and to indicate the degree on which they experiences each of 13 thoughts of feelings on a 5- point scale (0 not at all and 4 all the time).

- Amount of Adverse Events and/or Serious Adverse Events. Active capture during each site visit to assess specific symptoms and adverse events that are relevant to chronic knee pain or RF treatment.

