8.2 AEs, SAEs and SUSARs

8.2.1 Adverse events (AEs)

Adverse events are defined as any undesirable experience occurring to a subject during the study, whether or not considered related to the investigational intervention. All adverse events reported spontaneously by the subject or observed by the investigator or his staff will be recorded.

The potential risks to subjects in which a radiofrequency neurotomy procedure is performed, regardless of the treatment modality, may include the following, all of which are anticipated adverse events that have been identified as possible complications of procedures involving lesioning of nervous tissue:

- Infection,
- Damage to collateral nervous tissue,
- Increased pain,
- Failure of technique,
- Superficial burns,
- Damage to collateral tissue (i.e., bruising or hematoma),
- Deafferentation dysesthesia
- Paralysis
- Allergy

Subjects should be instructed to contact the investigator immediately if an AE occurs. At each visit, the investigator should further query the subject to determine if any new adverse events have occurred. Adverse events will be assessed and reported from the time the subject signs consent until study exit according to the following procedure.

Cocogen Trial

The investigator will assess the severity of each AE based on the following definitions:

Severity	Definition
Mild	An AE in which the subject is aware of signs or symptoms, but which does not
	interfere with the subject's usual activities of daily living, or is transient and
	resolves without treatment or sequelae.
Moderate	A sign or symptom which interferes with the subject's usual activities of daily
	living or requires treatment.
Severe	Any event listed as serious adverse event.

For each AE, the investigator will assess the causality/relationship to the received treatment according to the following criteria:

Relatedness	Definition
Possible	The association of the AE with the test article is unknown; other etiologies are also possible.
Probable	A reasonable temporal sequence of the AE with test article administration exists and based upon the medical professional's clinical experience, the association of the AE with the test article seems likely.
Definite	A causal relationship exists between the received treatment and the AE, and other conditions (e.g., concomitant illness, progression or expression of the disease state, reaction to concomitant medications) do not appear to explain the AE.

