9.2 Secondary study parameter(s)

All hypothesis testing will be explorative in nature, and thus secondary to describing the outcome measures. The confidence interval of the difference between groups will be used to test non-inferiority of conventional RF compared to cooled RF. In case the point estimate of the difference in proportion of treatment effect between groups will be below the non-inferiority limit, this will be suggestive of non-inferiority. In that case, we will use the results of this study to calculate the necessary sample size for a future randomized controlled non-inferiority trial.

Other secondary study parameters (MQS III, PGIC, duration of pain relief, OKS, the Timed Up and Go test, goniometry, HADS, PCS, EQ-5D-5L, performance of a TKA and the amount of Adverse Events and/or Serious Adverse Events) will be reported as mean or percentage difference including 95% confidence interval. Hypothesis testing will be performed using the independent t-test for continuous variables, and Fisher's Exact test for categorical variables. This will only be regarded as explorative in nature.

Cocogen Trial

COST EFFECTIVENESS ANALYSIS (CEA)

Economic evaluation comparing conventional to cooled RF treatment will be performed with a time horizon of 6 months. Cost-effectiveness will be assessed by evaluating the incremental cost-effectiveness ratios using several perspectives: societal cost per QALY (based on EQ-5D-5L), healthcare cost per reduced point on the pain score, and healthcare costs per additional treatment success. Standard bootstrap and sensitivity analysis will be performed to address uncertainty surrounding the findings.

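### Section 9 applies intention to treat and multiple imputation to every outcome, adverse events included, so AE counts need not be observed events in treated patients

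*Protocol*

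**What the plan says.** The opening of section 9 sets two general rules. On missing data: "Incomplete patients records will be imputed using multiple imputation to allow analysis on all randomised subjects". On the analysis population: "All outcome measures will be computed on the intention to treat sample".

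Section 7.1.2 lists "Amount of Adverse Events and/or Serious Adverse Events" as a secondary parameter. Section 9.2 puts it in the same list as the function, mood and quality-of-life scales, and that list closes with "the amount of Adverse Events and/or Serious Adverse Events) will be reported as mean or percentage difference including 95% confidence interval". The tests follow: "Hypothesis testing will be performed using the independent t-test for continuous variables", with Fisher's exact test for categorical variables. Their status is also stated: "This will only be regarded as explorative in nature".

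On collection, section 8.2.1 says: "Adverse events will be assessed and reported from the time the subject signs consent until study exit". The same section has the investigator rate each event's relationship to the treatment the patient actually received. Appendix E schedules AEs as an item at each follow-up from T1 to T4. The protocol defines no safety or as-treated set and does not exempt AEs from imputation.

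**The concern.** Intention to treat with multiple imputation is a reasonable default for effectiveness and cost outcomes. It suits safety counts poorly, for two reasons.

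- **Imputation.** An imputed AE is a model draw, not something that happened to a patient. With few events in 48 patients, even one or two drawn events are visible in the table. The informative summary is what was observed and over how much follow-up.
- **Denominator.** A patient who never has the procedure cannot have a procedure-related harm. Keeping that patient in the allocated arm's denominator lowers the apparent rate.

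Section 9 also fits poorly with section 8.2.1: one tabulates events by the arm assigned, the other judges them against the treatment given. The pilot is meant to mirror the future trial's design as closely as possible (section 1), and its data may be reused in that trial (section 11.1), so the rule could carry over.

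**Working it through.** **1. Is this fixed by the protocol or left open?** The steps are: all outcome measures use the intention-to-treat sample (section 9); AEs and SAEs are a listed secondary parameter (7.1.2) with a between-group comparison (9.2); and no exception appears anywhere. The rule therefore reaches AEs by its own terms. An analysis plan that treated AEs otherwise would depart from the protocol.

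**2. Can a record be incomplete for AEs?** Yes. AEs are a scheduled item at T1 to T4 (Appendix E), and patients may leave at any time (7.4). A missed visit or a withdrawal leaves the item blank, and incompleteness is what triggers imputation in section 9. No sentence says outright that AEs are imputed; this follows from an unqualified rule.

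**3. Can a patient be randomised and not treated?** Yes. Randomisation follows consent (7.2), and a patient may withdraw before the procedure (7.4). The protocol does not predict how often.

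**4. Sample size.** 12 per group × 2 arms × 2 populations = 48, as section 4.4 states. That is 24 per arm, so one patient is 1/24 = 4.2 percentage points of an arm's AE rate.

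**5. Imputed events (assumed rates).** Expected number in both arms together = 48 × dropout × AE rate. This treats a dropout's whole AE status as missing, so it overstates the number if part of the follow-up was seen.

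| Dropout | AE rate 5% | 10% | 20% | 30% |
|---|---|---|---|---|
| 5% | 0.12 | 0.24 | 0.48 | 0.72 |
| 10% | 0.24 | 0.48 | 0.96 | 1.44 |
| 20% | 0.48 | 0.96 | 1.92 | 2.88 |

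The range is about 0.1 to 2.9 events, below one in 9 of the 12 combinations.

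**6. Untreated patients (assumed counts).** Suppose an arm of 24 has 4 patients with an AE and 2 patients who were never treated. By allocation the rate is 4/24 = 16.7%; among treated patients it is 4/22 = 18.2%. The difference is 1.5 points, less than the 4.2 points that one patient represents.

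**The case against.** The strongest reply is that this is a point of wording with little practical effect. The AE comparison is exploratory, and the pilot's stated aims are effect estimates, inclusion rates and feasibility. There is one procedure, and sections 7.3 and 10.2 place it soon after consent and baseline, so untreated patients and pre-procedure events should be few. Individual events are still recorded and assessed for causality, and related SAEs go to the ethics committee, so observed harms are not lost. The choice of variables to impute is often left to an analysis plan. All of this stands as a limit on size. It does not remove the point, because the protocol states the population and the imputation rule for every outcome instead of leaving them open.

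A reader might infer more than the documents support:

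- **Device switches.** It is tempting to size the problem by a patient allocated to one device and treated with the other. The protocol describes no equipment failure or crossover, so such a figure would rest wholly on invention.
- **Failed localisation as a source of untreated patients.** Section 5.1 says "If all three target nerves were identified, a control fluoroscopy image is made to confirm the needle tip position", which can look like a route to abandoning treatment. However, the text has the transducer repositioned until a sensory threshold is reached and makes no provision for stopping. Such a patient has already had local anaesthetic and a cannula, and so would remain in any set defined by a started procedure.
- **Technique failure in the risk list.** Section 8.2.1 lists it for patients who undergo the procedure. It is not evidence of untreated patients.
- **Bias towards non-inferiority.** The non-inferiority question concerns pain. No safety margin or safety hypothesis is stated, so the charge that the AE rule favours the trial's conclusion does not hold.

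**Conclusion.** The point holds as a correction to a stated rule. As written, section 9 sends AEs and SAEs through intention to treat and multiple imputation, which gives a poorer safety summary than the data allow and sits awkwardly with the causality assessment in section 8.2.1. The sample size, the primary result and the non-inferiority comparison are unaffected.

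The practical effect is probably small. Every figure above rests on assumed AE, dropout and non-treatment rates, because the protocol gives none. The change is still worth making, since it is cheap and the pilot is meant to serve as a model for the larger trial.

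**What to change.** In section 9, restrict the intention-to-treat and imputation rules to effectiveness and cost outcomes. Then add a sentence on safety along these lines: *AEs and SAEs are summarised from observed events only, without imputation, by treatment actually received, in all patients in whom the RF procedure was started; the number of patients and the follow-up time are given per arm, and events between consent and the procedure are listed separately.* Section 9.2 can keep its exploratory comparison on that set.

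The cost is one or two sentences and no new data. The one downside is that AE denominators may be slightly smaller than the effectiveness denominators, which the table should state.

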9.1 Primary study parameter(s)

The primary outcome, the proportion of patients reporting treatment success at 3 months after treatment, will be described per group as count with percentage and 95% confidence interval. In addition, we will report the mean change from baseline on the NRS, including standard deviation and 95% confidence interval. Furthermore, we will compute the difference in proportion of success between groups and the difference in mean change from baseline between groups, both with 95% confidence interval. The lower bound of the 95% confidence interval of the difference will be compared to the non-inferiority limit. However, the latter part will be used only for exploratory purposes, due to the nature of the study design (i.e. pilot study).

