4.4 Sample size calculation

The primary aim of this study is to provide estimates of the effect sizes of the primary and secondary outcome measures, and to estimate the inclusion rate so that we have sufficient input to determine feasibility of a future RCT and to yield input for the sample size calculation. Further design aspects, such as the need for multilevel analysis based on clusters of patients within hospitals will be assessed as well. A rule-of-thumb suggests including 12 patients per group in case of a pilot study, so that preliminary data on effect sizes and feasibility can be obtained. (30) For our study, this means 12 patients in the conventional RF group and 12 in the cooled RF group, but separately for patients with osteoarthritis and for patients with knee pain after total knee arthroplasty. Hence, we will include a total of 48 patients.

Cocogen Trial

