7.2 Randomisation, blinding and treatment allocation

Final inclusion of a patient follows after written informed consent. Included patients will be subscribed by the central trial coordinator and the data management centre. The data management centre is responsible for the randomisation procedure, which will be performed with the software program CASTOR. Randomisation is justified because both treatments are similar with similar risks since the cooled radiofrequency is a modification of the conventional technique. The cooled radiofrequency however has the potential benefit of higher chance of therapy success (pain reduction) and longer duration of therapy success. Every patient from

Cocogen Trial

or the total knee arthroplasty group, or the osteoarthritis group, will be divided into one of the treatment groups at random so that half of every patient population (TKA and OA) received cooled and half conventional radiofrequency treatment. The randomisation ratio is 1:1. Patients in group 1 will receive conventional RF treatment, and patients in group 2 are being treated with cooled RF treatment.

The patients are treated by a pain physician who is not involved in the follow- up treatment. The blinding of each patient enrolled in this study is tested approximately 30 minutes after the treatment by asking the patient what they think they have received. At the 6 months follow- up, the patient is deblinded.

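### Sections 9.1 and 9.2 name unadjusted arm comparisons with no baseline covariate and no OA/TKA term; adjusting is a cheap precision gain whose size the protocol does not let one fix

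*Protocol*

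**What the plan says.** Section 9.1 sets the between-arm comparisons as "the difference in proportion of success between groups and the difference in mean change from baseline between groups", each with a 95% interval, and adds: "The lower bound of the 95% confidence interval of the difference will be compared to the non-inferiority limit". For the secondary outcomes section 9.2 states: "Hypothesis testing will be performed using the independent t-test for continuous variables", with Fisher's exact test for categorical ones. No baseline covariate and no population term is named in either section.

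The design is built around two populations. Section 4.4 starts from a rule of thumb ("A rule-of-thumb suggests including 12 patients per group in case of a pilot study") and applies it "but separately for patients with osteoarthritis and for patients with knee pain after total knee arthroplasty". Section 7.2 allocates "so that half of every patient population (TKA and OA) received cooled and half conventional radiofrequency treatment". In section 9, only the description of baseline characteristics is explicitly split by population.

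Section 7.1.2 defines MQS III, physical function (OKS, goniometry, Timed Up and Go), EQ-5D-5L, HADS and PCS as changes from baseline, and Appendix E collects all of them, and the NRS, at T0. PGIC and duration of pain relief have no baseline value.

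The comparisons are labelled exploratory: "All hypothesis testing will be explorative in nature, and thus secondary to describing the outcome measures". Section 2 says that the effect estimates will be used to size the later trial.

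**The concern.** A pilot's product is its estimates and their intervals. Where a baseline value has been collected, a raw change score fixes the coefficient on baseline at 1, whereas ANCOVA estimates it. In large samples ANCOVA is never less precise, and it can be much more precise. In the same way, a comparison that leaves out a factor by which allocation was balanced keeps the between-population variation in the standard error, so its intervals tend to be conservative.

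Two things are at stake. Intervals may be wider than 48 patients need give. And if the SD of raw change is carried into the next trial's sample size, that trial may be planned larger than an adjusted analysis would require.

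The wording also leaves the reader unsure whether the comparison is one of 24 against 24 or two of 12 against 12, because the protocol uses the word group both for treatment arms and for the OA and TKA populations.

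**Working it through.** **The plan's own figure.** 12 per arm × 2 arms × 2 populations = 48, which matches section 4.4 ("Hence, we will include a total of 48 patients"). The protocol gives no power, SD, correlation or success rate by population. Everything below therefore rests on assumed ranges.

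**Continuous outcomes: ANCOVA against raw change.** Let s0 and s1 be the baseline and follow-up SDs, k = s0/s1, and r their correlation.

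- Var(change) is proportional to 1 + k² − 2rk.
- Var(ANCOVA) is proportional to 1 − r².
- Saving = 1 − (1 − r²)/(1 + k² − 2rk). With k = 1 this is (1 − r)/2.

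| k | r = 0.3 | r = 0.4 | r = 0.5 |
|---|---|---|---|
| 1.2 | 47% | 43% | 40% |
| 1.0 | 35% | 30% | 25% |
| 0.8 | 22% | 16% | 11% |
| 0.6 | 9% | 5% | 1% |
| 0.5 | 4% | 1% | 0% |

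Example: k = 0.8, r = 0.3 gives 1 − 0.91/(1 + 0.64 − 0.48) = 1 − 0.91/1.16 = 22%.

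**Small-sample cost.** Estimating the baseline slope inflates the ANCOVA variance by about 1 + 1/(48 − 4) = 1.023. At k = 1 and 24 per arm, the saving becomes 1 − 0.65 × 1.023 = 33.5% at r = 0.3 and 1 − 0.75 × 1.023 = 23.3% at r = 0.5. With t quantiles, the interval half-width shrinks by 18% and 12%.

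**If the t-tests are on follow-up values instead.** Section 9.2 does not say which. The saving is then r²: 9% at r = 0.3 and 25% at r = 0.5.

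**What the NRS > 4 entry rule does.** Take s0 = s1 = 1 and r = 0.5, so the slope is 0.5, the residual variance is 0.75 and the saving is 25%. Now halve s0 by selection on baseline, which leaves the slope and residual variance unchanged.

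- Var(change) = 0.75 + 0.25 × (1 − 0.5)² = 0.8125.
- Var(ANCOVA) = 0.75.
- Saving = 0.0625/0.8125 = 7.7%. The correlation falls to 0.25/√0.8125 = 0.28.

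An illustrative simulation points the same way. It used integer NRS, baseline limited to 5–10, 24 per arm, and SDs of 1.3 at baseline and 2.5 at follow-up before rounding and clipping. It gave a saving of about 3% at r = 0.3 and a loss of 0.5% to 2.5% at r = 0.4–0.6.

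**Success proportion: stratified against pooled.** With equal-sized populations, saving = 1 − (mean of the two p(1 − p))/(p̄(1 − p̄)), where p̄ is the average success rate.

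- 50% and 50%: 0%.
- 60% and 40%: 1 − 0.24/0.25 = 4%.
- 60% and 35%: 1 − 0.23375/0.249375 = 6%.
- 65% and 30%: 1 − 0.21875/0.249375 = 12%.

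**Pooled or separate.** At 50% success in both arms, the approximate 95% half-width is 1.96 × √(2 × 0.25/24) = 28 points for 24 against 24, and 1.96 × √(2 × 0.25/12) = 40 points for 12 against 12.

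**The case against.** Change scores, t-tests and Fisher's exact test are valid in a randomised trial, the comparisons are exploratory, and the sample size makes no power claim. Covariates and strata are often settled in a statistical analysis plan, which is not at hand. This fixes the level of the point: it is about efficiency and clarity, not validity. It does not remove it, because the protocol does not stay silent; it names specific unadjusted methods.

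A reader might go further in four ways that the document does not support.

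- That baseline is ignored. It is not: change scores and the 50% responder definition both use it. What is missing is adjustment for it.
- That 25–35% of the information is lost. That range needs r = 0.5–0.3 and equal SDs, and the protocol gives neither.
- That the NRS > 4 entry rule makes raw change especially inefficient. The calculation above shows the reverse: a narrower baseline spread shrinks the gain, and for NRS it may be nil. Sections 4.2 and 4.3 set no such cut-off on the other outcomes, so more similar SDs are plausible there.
- That OA and TKA will be pooled into one figure. Section 9.1 does not say so, and the separate sizing in section 4.4 suggests that population-specific results are wanted. The text leaves it open.

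Chance baseline imbalance is not a separate harm either. Under randomisation the raw difference is unbiased, and such imbalance is already part of the variance compared above.

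**Conclusion.** The point stands as an inexpensive improvement to an exploratory analysis. The protocol sizes and allocates by OA and TKA and collects baselines for most continuous outcomes, yet the comparisons it names use neither as an adjustment.

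The absence of the terms is certain from the text; the size of the gain is not. Over the assumed range of r = 0.3–0.5 it runs from roughly nothing for a restricted outcome such as NRS to about a third of the variance for an outcome with similar spread at baseline and follow-up, and higher still if the baseline spread is the larger. For the primary success proportion it is small unless the two populations respond very differently, and the gaps of 25 and 35 points behind the 6% and 12% figures are assumptions.

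**What to change.** - **Continuous outcomes with a baseline** (NRS, OKS, Timed Up and Go, goniometry, MQS III, EQ-5D-5L, HADS, PCS): in sections 9.1 and 9.2, estimate the treatment difference by ANCOVA of the follow-up value on treatment, the outcome's own baseline and OA/TKA. Keep raw changes as description. Leave PGIC and duration of pain relief out of the baseline adjustment.
- **Success at 3 months:** report a Mantel-Haenszel risk difference stratified by OA/TKA. Choose a 95% interval method that can be combined across the multiple imputations planned in section 9. Show the OA and TKA estimates side by side, so that the basis of each figure is plain.
- **For the later trial:** report the baseline/follow-up correlation and the residual SD alongside the SD of change.

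The cost is two model degrees of freedom (residual 44 instead of 46), a few percent of variance at most, so a negligible loss for NRS is possible. There is slightly more analysis work, mainly in combining the stratified interval with the imputations when cells hold about 12 patients. Nothing changes in recruitment, visits or data collection.
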